hdEEG. The stroke hdEEG-processing will follow the steps as outlined above. In particular to stroke, we will additionally 1) perform spectral analysis to identify regions with EEG slowing (i.e., stroke region(s)), 2) use SSEP to assess sensorimotor function, and 3) investigate a novel algorithm, called EEG-No Source Imaging (NSI), which aims to localize the stroke through a hypothesis testing approach.

EIT. The collected EIT data will be used to construct 3D images of electrical properties within the head using single- and multi-frequency image reconstruction approaches. The reconstructions rely on a 3D tetrahedral mesh of the domain; nominal and patient-specific meshes will be considered. We will utilize the FreeSurfer-segmented data for this effort. We will consider reconstructions with and without structural information, e.g. skull, CSF, and stroke boundaries. Algorithms will also be considered that incorporate both EEG and EIT information. Electrical properties of the stroke, penumbra, and other ROIs will be considered for analysis.

EIS. The EIS data will look at raw impedance magnitudes and spectral properties of the acquired multi-frequency traces. Phase, magnitude, resistance, reactance and spectral fitting metrics will all be extracted

from the signals and explored in the development of a novel algorithm to isolate an intracranial abnormality, e.g., stroke region(s). This processing will include analysis of the heterogeneity of the surface potentials and will be compared to prior patient imaging to test the ability to detect, identify and localize stroke. Data will be explored in three cohorts: 1) all stroke vs all healthy 2) all ischemic vs all hemorrhagic and 3) large vs small infarct. Potential augmentation of EIS signals with EIT or EEG traces will be explored as well.

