8. Placebo Use or Inconsistency with Standard of Care

Does any part of this study involve the use of a placebo or procedures that are inconsistent with the standard of care at Dartmouth-Hitchcock Medical Center?

No Yes

If Yes, explain how the use of placebo or non-standard of care therapy may affect risks for participants, addressing the following:

- The safety and efficacy of other available therapies
- The maximum total length of time a participant may receive placebo on study
- The greatest potential harm that may result from not receiving or delaying effective therapy
- Safeguards for the participants receiving placebo or non-standard of care therapy

9. Genetics

Does any part of the study involve genetic analysis of biological specimens?

No

Yes, the study is based on the premise that a link between a genotype or a biomarker and a specific disease or condition is clinically useful in predicting the development of that specific disease or condition.

Please complete the [Genetic Research Form](#) and upload it to the ‘Supporting Documents’ page in Report.

-OR -

Yes, the study is looking for an association between a genotype or a biomarker and a specific disease or condition, but at this point it is not clear if the genetic marker has predictive value. The uncertainty regarding the predictive value of the genetic marker is such that studies in this category will not involve referral of participants to genetic counseling; however, participants will be informed of genetic testing in the consent form. **Please comment:**

10. Equitable Participant Selection

a. Estimated number of participants at Dartmouth CPHS reviewed sites:

For the short-term hdEEG study: 100 epilepsy patients, 15-20 brain tumor patients and 15-20 normal controls. For the short-term stroke study: 50 EIT/EIS-measured patients with 50 controls. For the long-term study: 20 epilepsy patients. For the peripheral nerve study: 20 subjects.

b. Provide a justification of the proposed sample size

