After completing pilot studies, we will focus on those tests which appear to be eliciting consistent, localized brain activation. Under these circumstances adequate statistical power should be obtained by repeating these tests in 15-20 patients. However, for the short-term epilepsy study we are more interested in investigating the correlation between the spike localizations and other clinical diagnostic results. Due to their very deep location, the determination of spike localization could be challenging in some epilepsy patients. In order to have a better understanding of the efficacy of using high-density EEG to provide useful information for various types of epilepsy patients (i.e., temporal vs. extra-temporal), we would like to perform this study on a larger patient size.

For the EIT/EIS cohort, sample size is based on previous contrasts observed in ex-vivo ischemic and hemorrhagic tissue [a]; specifically, the conductivities at 1 kHz were 0.075 Siemens/meter (S/m) for hemorrhagic tissue and 0.11 S/m for ischemic tissue. For a reported standard deviation of 0.025 S/m, there would be a 95% power to detect significant differences through an unpaired t-test with a group sample size of ten subjects for each cohort (20 total). An initial investigation into non-invasive in-vivo signals results in an ~50% drop in signal, requiring a 2x increase in sample size and a total desired cohort of n=50, split into two sub-cohorts of n=25 ischemic and hemorrhagic stroke, respectively. However, as this is a pilot study, these are projections; should initial data indicate higher signal contrast and lower standard deviations than anticipated, the numbers will be revisited to ensure optimized patient recruitment.

[a] Yang, L., Zhang, G., Song, J., Dai, M., Xu, C., Dong, X., & Fu, F. (2016). Ex-Vivo Characterization of Bioimpedance Spectroscopy of Normal, Ischemic and Hemorrhagic Rabbit Brain Tissue at Frequencies from 10 Hz to 1 MHz. *Sensors (Basel, Switzerland)*, 16(11).

c. Define the target population:

Epilepsy patients

Patients with a diagnosis of epilepsy will be considered for participation if they are interested and in the judgment of the research team they require further mapping or are capable of performing the functional and/or cognitive tasks required of the study.

Inclusion criteria:

1. Able to perform the tasks
2. Subject or legally authorized representative able to provide appropriate consent

Exclusion criteria:

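### The stroke-cohort sample-size arithmetic does not follow from its inputs: 10 per group gives 84% power (two-sided 5%), not 95%, and a halved contrast at unchanged SD needs about 4 times the patients, not 2

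*Combined protocol and SAP*

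**What the plan says.** Section 10.b of the combined protocol and SAP takes its inputs from a cited study of excised rabbit brain tissue, "Ex-Vivo Characterization of Bioimpedance Spectroscopy of Normal, Ischemic and Hemorrhagic Rabbit Brain Tissue". It reports that "the conductivities at 1 kHz were 0.075 Siemens/meter (S/m) for hemorrhagic tissue and 0.11 S/m for ischemic tissue". It continues "For a reported standard deviation of 0.025 S/m", and concludes that "there would be a 95% power to detect significant differences through an unpaired t-test with a group sample size of ten subjects" in each cohort, 20 in total. Neither alpha nor sidedness is stated.

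It then turns to early in-vivo work which, it says, "results in an ~50% drop in signal, requiring a 2x increase in sample size and a total desired cohort of n=50". That total is divided equally: 25 ischemic and 25 hemorrhagic patients. No in-vivo SD is given, 'signal' is not defined, and no power is quoted for 25 per group. The section adds: "However, as this is a pilot study, these are projections". It provides for revisiting the numbers if contrast is higher and SDs are lower than anticipated.

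Section 10.a carries the figure forward: "For the short-term stroke study: 50 EIT/EIS-measured patients with 50 controls". Section 4 (EIS) lists "all ischemic vs all hemorrhagic" among the comparisons to be explored.

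**The concern.** This is the only computed power statement in the document, and the 25 + 25 split rests on it. Two steps look wrong. The power quoted for 10 per group is higher than the stated means and SD can give at conventional 5% levels. The inflation step treats sample size as proportional to 1/difference, whereas it is proportional to 1/difference squared.

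Because the text starts at 95% and then adjusts n for the weaker signal, a reader will naturally take 50 patients as still carrying about 95% power to separate the two stroke types. If the true power is much lower, a null ischemic-versus-hemorrhagic result could be misread as evidence against EIT/EIS. The provision for revisiting n covers only better-than-expected data, so nothing in the section addresses the case in which the shortfall would bite.

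**Working it through.** **Inputs (section 10.b).** Means 0.075 and 0.11 S/m; SD 0.025 S/m; unpaired t-test; 10 per group, then 25 per group; signal drop about 50%. **Assumptions.** Alpha 5%, two-sided, with one-sided alongside; equal variances; no dropout.

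**Method.** d = difference/SD. Power is the probability that a noncentral t with 2n − 2 degrees of freedom and noncentrality d × √(n/2) exceeds the critical value.

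**Step 1: the 95% figure.**
- d = (0.11 − 0.075)/0.025 = 1.40.
- With n = 10: noncentrality 1.40 × √5 = 3.13; df 18; critical t 2.10 two-sided, 1.73 one-sided.
- Power is 84.1% two-sided and 91.4% one-sided. A simulation of 200,000 trials gives 84.2% two-sided. The normal approximation gives 87.9% and 93.1%.
- The plan's 95% is not reproduced. With 10 per group it would need alpha of about 0.16 two-sided (0.08 one-sided), or an SD of at most 0.0205 S/m (0.0229 one-sided).
- At SD 0.025, n = 14 gives 94.6% and n = 15 gives 95.9%, so 95% needs 15 per group (12 one-sided).

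**Step 2: the doubling.**
- Required n is proportional to 1/d². Halving the difference at the same SD multiplies n by 1/0.5² = 4.
- With exact t calculations at d = 0.70, 95% power needs 55 per group (n = 54 gives 94.99%, n = 55 gives 95.3%). That is 55/15 = 3.7 times; one-sided, 45 per group.
- A doubling fits a drop of 1 − 1/√2 = 29%.
- Twice 20 is 40, whereas the plan states 50, which is 2.5 times. That factor fits a drop of 37%. No reason is given for the extra 10.

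**Step 3: what 25 per group delivers.** Difference 0.035 × 0.5 = 0.0175 S/m, with the in-vivo SD varied because the plan does not give it:

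| Assumed in-vivo SD (S/m) | d | Power, two-sided 5% | Power, one-sided 5% | n per group for 95%, two-sided |
|---|---|---|---|---|
| 0.0125 | 1.40 | 99.8% | 99.9% | 15 |
| 0.0175 | 1.00 | 93.4% | 96.7% | 27 |
| 0.020 | 0.875 | 85.8% | 92.0% | 35 |
| 0.025 | 0.70 | 67.9% | 78.7% | 55 |
| 0.030 | 0.583 | 52.4% | 65.1% | 78 |

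- 25 per group reaches 95% for 0.0175 S/m only if the SD is at most 0.0168 S/m (0.0185 one-sided).
- At SD 0.025, the difference detectable with 95% power is 1.041 × 0.025 = 0.026 S/m (one-sided 0.944 × 0.025 = 0.024).
- A literal doubling, 20 per group, gives 57.8% at SD 0.025 (two-sided).

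**Step 4: other readings.**
- If 'signal' means signal power, the contrast falls by 29% and d = 1.40/√2 = 0.99. Then 25 per group gives 92.9%, and 95% needs 28 per group.
- If 95% at 10 per group is simply granted (d = 1.71 two-sided, 1.53 one-sided), halving d leaves 25 per group with 84% two-sided or 85% one-sided; 95% needs 37 or 38 per group.

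**The case against.** Five points can be made for the plan.

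**Rounding.** The ischemic mean is printed to two decimals. Varying all three inputs within rounding moves two-sided power at 10 per group between 69% and 94%, so the two-sided shortfall survives. A one-sided 5% test would reach 95% if the unrounded ischemic mean were about 0.1133 S/m (difference 0.0383, d = 1.53). That reading needs both an unstated one-sided test and an unprinted mean. It stands only as a reason to state the inputs more precisely.

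**Undefined signal.** If attenuation shrinks the SD in step with the mean difference, d stays at 1.40 and no increase is needed. This is a fair limit: the fourfold figure holds only at an unchanged SD. It does not justify a doubling, though, which would require the SD to fall by a factor of about 1.41 while the difference halves, and the plan does not say that it does.

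**No power is claimed for 25 per group.** True; the carried-over 95% is an implication. The 68% also combines both steps, and correcting only the second gives about 84%.

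**The t-test is not the planned analysis.** Section 4 (Statistical Analyses) assigns stroke-type discrimination to ROC methods and names no t-test on conductivity. So 68% is the power of the test used for sizing, not of the ROC analysis. That limits its meaning but does not correct the stated figure.

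**Pilot status.** The plan calls its numbers projections. This supports keeping 50 patients and lowers the stakes, but a projection still has to follow from its inputs.

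**Conclusion.** The concern holds. On the printed inputs, 10 per group gives 84% power at two-sided 5% and 91% at one-sided 5%, not 95%. Doubling n for a halved signal is wrong if the mean difference halves and the SD is unchanged; the factor is then about 4. It also does not lead to the stated total of 50.

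Under that reading, the planned 25 per group carries about 68% power two-sided (79% one-sided). This figure rests on an in-vivo SD of 0.025 S/m taken over from ex-vivo rabbit tissue, so it is a conditional result and not proof that the cohort is too small. What is established is that the derivation does not support the sample size. The error should be corrected, but it does not call for a different n in a study that describes itself as a pilot.

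**What to change.** Keep 50 stroke patients. In section 10.b, remove the statement that a doubling is required, and replace the power passage with wording such as:

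> With 10 per group, an unpaired t-test (two-sided 5%) has 84% power for a difference of 0.035 S/m at SD 0.025 S/m; 95% power needs 15 per group. In vivo we assume that the difference in mean conductivity falls by about 50%, to 0.0175 S/m. The in-vivo SD is not known. With 25 per group (two-sided 5%), power is 93% at SD 0.0175, 86% at 0.020, 68% at 0.025 and 52% at 0.030 S/m. At SD 0.025 the difference detectable with 95% power is 0.026 S/m. The total of 50 is a pilot size.

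The sponsor should first confirm what fell by 50%. If it was not the mean difference, the text should say so and give the matching figure; for signal power that is 93% at SD 0.025. If a one-sided test was intended, the one-sided figures should be used and the choice stated.

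The cost is a protocol wording change, with no effect on enrolment, procedures or analysis. The 95% claim goes, and 50 then rests on the pilot rationale. Keeping 95% at a halved difference and SD 0.025 would take 2 × 55 = 110 stroke patients, which is not proposed here.
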